### **2.3 Primary Endpoints**

The primary endpoint will be evaluation of toxicity, adverse events and reportable serious adverse events, i.e. grade 3 or higher, as defined by the NCI Common Toxicity Criteria for Adverse Events (CTCAE v. 5.0). RTOG/EORTC Radiation Toxicity Grading is standard of care at Beaumont Hospital for all radiation patients and CTCAE is the standard for reporting & publications. These criteria comprise of various parameters, including performance status, motor function, sensory function, general mental status, nausea/vomiting, hearing loss, xerostomia, and skin toxicity [51]. The CTCAE are cancer-specific and will be supplemented by information from neurocognitive testing using MMSE and ADAS-Cog. The tests will be administered by an appointed, trained site professional at baseline and at 6 weeks, 3 months, 6 months, and 12 months during follow-up. In the context of radiation oncology, the optimal time period for assessing cognitive impairment is within >6 months to 1 year [52,53].

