### **3.9. Radiation On-Treatment Monitoring and Adverse Events**

Radiotherapy will be continued without interruption if at all possible as prescribed. If the sum of total radiotherapy interruptions exceeds seven normally scheduled treatment days, the treatment will be considered an unacceptable deviation from the protocol. This patient should

be reported to the principal investigator, and the patient will not be considered for final data analysis. Patients who do not complete a complete, total course of study radiotherapy will be replaced in the study in order to have 15 evaluable patients in each arm.

Patients will be monitored weekly by the treating radiation oncologist for the duration of radiotherapy and at regular intervals following radiotherapy. Scheduled post treatment visits are at 6 weeks, 3, 6 and 12 months. At each visit, the patient will undergo an interval history and physical exam and completion of Common Terminology Toxicity Criteria (Version 5.0), and RTOG toxicity scoring to assess any toxicity associated with this study. The RTOG toxicity scoring is done as radiation/oncology standard of care at Beaumont. This will include not only the effects on the CNS but any general adverse effects which may or may not be related to the treatment delivered. Each patient will be assigned a baseline score for skin, eye, ear and CNS and this will be monitored and evaluated during and after treatment for both acute and late toxicity. All adverse events will be recorded on an Adverse Event Reporting Form. The known risks associated with whole brain irradiation at the dose levels described may include, but are not limited to 1) hair loss, 2) decreased hearing, 3) nausea, 4) vomiting and 5) visual changes and 6) skin reactions. The grade or severity of adverse event that is common with the planned radiation dose for this trial based on the RTOG Common Toxicity Criteria are skin (Grade 1), CNS (Grade 1), ocular (Grade 0) and brain (Grade 1). All related/possibly related Grade >3 Toxicities will be reported as unexpected in severity to the IRB and monthly to the DSMB.

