If at any time during the study there is an increase of 2 or more points, an evaluation by the DSMB will take place within the week to determine if it is therapy related or due to other non-study related events. Should this happen during the course of the treatment, therapy will be immediately stopped and all medical attempts will be made to correct the cause of the noted decline. The records and information related to the event will be reported to the IRB and the FDA using standard reporting mechanism. If it is determined that the toxicity was not study related accrual will resume once cleared by IRB.

Supportive management of symptoms (e.g., the use of oral or intravenous steroids for brain edema and the use of antiemetics) is permitted at the discretion of the treating radiation oncologist, neurologist or neurosurgeon.

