### **3.12 Stopping Rules**

This study will be stopped for any of the following reasons

- 1) Any patient death attributed to treatment
- 2) Any patient who develops a Grade IV adverse event
- 3) More than 3 of 15 patients who develop a Grade 3 adverse event as per CTCAE v.5.0 in either group
- 4) 50% or more patients in either group have no change or increase in amyloid based on Amyvid PET Scan

- 5) 5 patients that show greater than 4 point deterioration in MMSE in two consecutive cognition evaluations
- 6) 5 patients that show increases greater than 7 on ADAS-Cog scale.

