#### **5.0 Data Safety Monitoring Plan**

The appointed Data Safety and Monitoring Board (DSMB) will act in an advisory capacity to the IDE Sponsor/Investigator and the Beaumont Research Institute to monitor participant safety, data quality and evaluate the progress of the study.

The DSMB will consist of four members (three voting, one non-voting) who are not directly involved in the trial and have expertise in the fields of radiation and/or Alzheimer's disease management, clinical trial methodology, and/or biostatistics. Prior to implementation of the protocol, the DSMB will meet to review the protocol and informed consent documents, approve templates for study summary reports, and to adopt the charter.

The DSMB will review cumulative study data to evaluate safety, study conduct, and scientific validity and integrity of the trial. Meetings of the DSMB may occur as frequently as monthly during the enrollment and treatment phase of the trial. Monthly meetings will be scheduled, however, prior to each meeting, the DSMB Chair will review the agenda. If there are no new enrollments, additional study data, or updates from the IDE Sponsor/Investigator, the DSMB Chair may cancel the meeting.

After enrollment has stopped, the DSMB will meet quarterly. The DSMB will discharge itself from its duties when the last participant completes the study.

The DSMB Chair will provide a written report after each meeting containing DSMB recommendations as to whether the study should continue without change, be modified, or terminated. The DSMB Chair will provide the written report to the IDE Sponsor/Investigator and the Beaumont Research Institute. The IDE Sponsor/Investigator will submit the report to the Site Investigator(s) and the FDA. The Site Investigator(s) will submit the reports to their respective IRBs.

Along with meeting at regular intervals during the conduct of the trial, the DSMB will meet within one week of any adverse event that increases by 2 or more points according to the

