**CNS Toxicity:**

**Fatigue**

- Grade 0, None
- Grade 1, Fatigue relieved by rest
- Grade 2, Fatigue not relieved by rest; limiting instrumental ADL
- Grade 3, Fatigue not relieved by rest, limiting self care ADL

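### On the visible text, a worsening from Grade 2 to Grade 3 reaches the level of the primary endpoint and stopping rule 3 but does not trigger the one-week DSMB review

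*Combined protocol and SAP*

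**What the plan says.** Section 3.9 sets the reference point: "Each patient will be assigned a baseline score for skin, eye, ear and CNS", which is then followed during and after treatment. The next paragraph holds the urgent trigger: "If at any time during the study there is an increase of 2 or more points, an evaluation by the DSMB will take place" within a week, to judge whether the change is related to therapy. That paragraph also ties to the trigger the stopping of therapy if the rise occurs during treatment, a report to the IRB and FDA, and the resumption of accrual after IRB clearance.

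Section 5.0 repeats the rule in different terms: "the DSMB will meet within one week of any adverse event that increases by 2 or more points". The sentence breaks off there in the text available to this review, and what follows it could not be read.

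Other safety provisions use the absolute grade:

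- Section 2.3, primary endpoint: "reportable serious adverse events, i.e. grade 3 or higher".
- Section 3.12, rule 2: "Any patient who develops a Grade IV adverse event".
- Section 3.12, rule 3: "More than 3 of 15 patients who develop a Grade 3 adverse event as per CTCAE v.5.0 in either group".
- Section 3.9, reporting: related or possibly related toxicities of Grade >3 go to the IRB, and monthly to the DSMB.

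For routine review, the Schema has the DSMB meeting monthly on all new data for patients under treatment or in follow-up. Section 5.0 schedules monthly meetings, lets the Chair cancel one if there is nothing new, and moves to quarterly meetings once enrolment has stopped. The Appendix III worksheet grades 12 separate items, grouped as skin, eye, ear and CNS.

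**The concern.** The urgent trigger measures change, while the endpoint and stopping rule 3 measure level. The two can disagree in an unhelpful direction. A patient going from Grade 0 to Grade 2 stays below the endpoint level but prompts a DSMB evaluation within a week. A patient going from Grade 2 to Grade 3 has an event that counts toward the safety conclusion but prompts none.

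What is at stake is the timing of the relatedness judgement. In a first study of whole-brain irradiation for this indication, with toxicity as the primary endpoint, the DSMB would want to look promptly at the events that move the trial toward rule 3.

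The unit of the rise is also unclear. A baseline score per site and a rise per adverse event can give different answers for the same patient.

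**Working it through.** **The plan's own figures.** No number in the plan bears directly on this trigger. The sample-size limits in section 3.1 for 0 events in 15 patients reproduce as 1 − α^(1/15): 26.44%, 18.10% and 14.23%, against the stated 26.4%, 18.1% and 14.2%. The point does not depend on them.

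**Step 1. Which worsenings fire?** Inputs: the rule rise ≥ 2 (3.9, 5.0) and absolute Grade 3 (2.3, 3.12). Points are read as grades, and the rise is taken from baseline.

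| Baseline to later grade | Rise | One-week review | Grade 3 or higher |
|---|---|---|---|
| 0 to 2 | 2 | yes | no |
| 0 to 3 | 3 | yes | yes |
| 1 to 3 | 2 | yes | yes |
| 2 to 3 | 1 | no | yes |
| 2 to 4 | 2 | yes | yes (rule 2 also stops the study) |
| 3 to 4 | 1 | no | yes (rule 2 also stops the study) |

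So 2 to 3 is the only route to a new Grade 3 that the trigger misses. If the rise were counted between visits instead, 2 to 3 would still be +1, and a stepwise 0, 1, 2, 3 would also be missed.

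**Step 2. Which worksheet items are involved?** Highest grade offered in Appendix III:

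- Six end at 4: radiation recall reaction, cataract, hearing loss, motor neuropathy, sensory neuropathy, vomiting.
- Five end at 3: xerostomia, blurred vision, ear pain, fatigue, nausea.
- One ends at 2: alopecia.

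Items able to rise by 2 or more from baseline 0, 1, 2 and 3 number 12, 11, 6 and 0. From baseline Grade 2, the six that can fire do so only at Grade 4, where rule 2 already applies. The five that end at Grade 3 cannot fire at all. Alopecia has no Grade 3 and is not part of the gap.

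**Step 3. Can a patient start at Grade 2?** Yes. The eligibility criteria in 3.3.2 do not exclude hearing loss, cataract or fatigue. The fatigue anchor, for instance, is "Grade 2, Fatigue not relieved by rest; limiting instrumental ADL". The documents give no prevalence, so it is assumed here. With a proportion p of patients starting at Grade 2 on some item, P(at least one of 15) = 1 − (1 − p)^15:

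- p = 5%: 53.7%
- p = 10%: 79.4%
- p = 20%: 96.5%
- p = 30%: 99.5%

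This is the chance that someone is exposed to the gap, not that a review is missed. The expected number missed is 15 × p × q, where q is the chance that such a patient then reaches Grade 3 on that item. Over this range 15 × p runs from 0.75 to 4.5 per group. The documents give no value for q, so the number missed can only be said to be smaller.

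**Step 4. How many could accrue?** Rule 3 needs more than 3 of 15, that is 4. Up to three patients per group could go from 2 to 3 with neither a one-week review nor a stop.

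**Step 5. Which unit?** Take baseline fatigue Grade 2 and new vomiting Grade 3, both CNS items. Per event (5.0), vomiting rises from 0 to 3, which is +3 and fires. If the CNS site score in 3.9 is the worst item at that site, it rises from 2 to 3, which is +1 and does not fire. The protocol does not say how a site score is formed.

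**The case against.** The strongest reply is that a change-from-baseline trigger beside absolute endpoints is not a contradiction, because it keeps pre-existing impairment from setting off urgent reviews. Other safeguards remain. Patients are seen weekly during radiotherapy, Grade 3 events are recorded and count toward rule 3, and the DSMB sees all new data at routine meetings. During enrolment the practical loss is a review within about a month instead of a week. The quarterly interval in 5.0 applies only after enrolment has stopped, when little or no irradiation remains, and the Schema describes monthly review that includes follow-up. All of this stands, and it limits the point to one of delay. It does not explain why a rise from 0 to 2 is urgent while a rise from 2 to 3 is not.

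A reader might also infer more than the documents support:

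- **That the 2-point rise is the only trigger for urgent review.** This cannot be confirmed, because the 5.0 sentence is cut and its continuation was not available.
- **That a high baseline at a site hides new toxicity there.** This is one reading of 3.9. The wording of 5.0 is per event, and on that wording the vomiting example fires.
- **That patients with MMSE 10–20 will often start at Grade 2.** The anchors require a specific symptom, such as hearing loss or unrelieved fatigue. Loss of daily function from dementia does not itself score. Some neurological and scalp conditions are also excluded.
- **That every patient with a baseline Grade 2 item is affected.** The gap matters only if that item, or on the site reading its site, then reaches Grade 3.
- **That 3 to 4 is a further gap.** Rule 2 already stops the study at Grade IV.

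**Conclusion.** The point holds as a cheap improvement. On the visible text, the one-week review misses a worsening from Grade 2 to Grade 3, the level used by the primary endpoint and stopping rule 3, and the Grade >3 monthly report does not cover Grade 3 as written. The consequence is a delayed relatedness review, not an unrecorded event. Up to three such patients per group could accrue without a prompt review before the fourth meets rule 3. How often this would happen cannot be estimated from the documents.

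The conclusion assumes that points mean grades, that the rise is taken from baseline, and that the missing end of the 5.0 sentence adds no absolute-grade condition. Separately, 3.9 and 5.0 disagree on the unit, and that needs settling whatever the prevalence of baseline Grade 2.

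**What to change.** First check the full sentence in section 5.0. If it adds no absolute-grade condition, the sponsor should reconcile sections 2.3, 3.9 (the reporting sentence and the 2-point paragraph), 3.12 and 5.0 so that:

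- the trigger for the one-week DSMB review is consistent with the absolute grade used by the endpoint and stopping rule 3;
- the rise is read per adverse event, against that item's own baseline grade, with the scale and reference point named;
- 3.9 and 5.0 use the same unit.

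Section 3.9 also ties the stopping of therapy to this trigger. That sentence, and any clinical threshold, should be left to the clinical team to reconcile; none is proposed here.

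The cost is a short amendment. The 12 items are already on the worksheet, and the Study Calendar already has a pre-treatment toxicity evaluation. The downside is a few extra DSMB reviews: rises from 0 to 3 and from 1 to 3 already fire, so the additional Grade 3 reviews would come from patients starting at Grade 2, at most three per group before rule 3 is met.

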### **3.10. Cognitive Assessment and Quality of Life Assessment During Treatment**

The Mini Mental Exam and ADAS-Cog are the two most commonly used tests of cognition in Alzheimer's Disease [58]. After treatment these tests will be administered by study designated, trained professional at 6 (+1) weeks, 3 (+1) months, 6 (+1) months and 12 months. Given that the ADAS-Cog is not used routinely in clinical practice (but rather a research assessment) and that the personnel involved may not necessarily be doing other studies requiring ADAS-Cog, it will not be possible to blind the professional doing the testing. The ADAS-Cog yields a single score that reflects the arbitrary weighting of performance in several cognitive domains including learning, language and spatial cognition but does not address executive function. A normal score for someone who does not have Alzheimer's or another type of dementia is 5; the greater

the dysfunction, the greater the score [59]. The properties of the ADAS-Cog are well understood; there is a curvilinear relationship between disease severity and rate of change on the ADAS-Cog. In a large clinical trial the baseline score for placebo-treated patients in the ADAS-Cog range of 13 to 26 was  $24.2 \pm 9.4$  and this increased to  $29.9 \pm 13.7$  representing a decline of  $5.7 \pm 8.2$  points over 1 year [60]. In this trial, a significant benefit in the active group was considered to be a 50% reduction in cognitive decline as indicated by change in ADAS-Cog score compared with the placebo group. In this study, patients who have an increase of no more than 50% (~3 points) on the ADAS-Cog at the end of treatment will be considered responders. This is equivalent to a delay in decline of about 6-8 months. Longitudinal analysis will be carried out for each individual patient using a fixed quadratic effect of time, dependent on the baseline level of ADAS-Cog, i.e., an interaction of baseline ADAS-Cog and the quadratic component of time.

The MMSE is a commonly used 30-point scale for assessing cognitive function in the domains of orientation, registration, attention and calculation, recall, language, and praxis. A MMSE score of 10 to 20 suggests moderate dementia. On average, the MMSE score of a person with moderate dementia declines about three to four points in a 12-month period. A similar analysis to that described above for the ADAS-Cog test will be carried out taking into account time and baseline MMSE score.

Completion of Quality of Life indices (Quality of Life-AD and QUALID Scale) analysis will be completed by PI designated research staff at the same visit for cognitive testing.

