### **2.4 Secondary Endpoints**

- 1) Neurocognitive testing will be used to assess changes in cognitive function using the MMSE and ADAS-Cog. The tests will be administered by an appointed, trained site professional at baseline and at 6 weeks, 3 months, 6 months, and 12 months during follow-up.
- 2) Quality of life will be monitored via questionnaires completed by the patient prior to the start of irradiation and at 6 weeks, 3 months, 6 months, and 12 months during follow-up. Specific questionnaires include the QOL-AD and QUALID, which have been established as sensitive measures of various parameters of quality of life.
- 3) A pretreatment and post treatment (4 months) Amyvid PET/CT scan will be carried out to determine if there are any correlations between neurocognitive /QOL test results and amyloid number, size and location and changes after treatment.

[figure not shown]

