#### **3.8.4. Dose Prescription and Delivery**

The prescription point in the cranial volume is at or near the center. NOTE: regardless of the location of the central axis, the dose should be prescribed at the center on the cranial volume (midway between the maximum separations). The total dose to the prescription point will be 10 Gy for the initial 15 patients then 20 Gy for patients 16-30. This dose will be delivered in 5 fractions or 10 fractions of 2 Gy. All radiation fields shall be treated once each day. The treatment shall be given 5 days a week. No corrections for bone attenuation shall be made. The dose variations in the target volume shall be within +7% (- 5% of the prescription-point dose). No corrections shall be made for treatment interruptions less than 3 days. For interruptions greater than seven days, please contact the site PI.

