## 6.0 Study Calendar

	Pre Treatment	Daily Radiation Treatment	6 Weeks Post Treatment +/- 1 week	Post Treatment (Months)			
				3 +/- 2 weeks	4 +/- 2 weeks	6 +/- 2 weeks	12 +/- 2 weeks
ADAS-Cog	X		X	X		X	X
MMSE	X		X	X		X	X
History & Physical	X		X	X		X	X
AMYViD PET scan	X				X		
Toxicity Evaluation	X	X	X	X		X	X
QOL-AD and QUALID	X		X	X		X	X

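### The ADAS-Cog responder rule is tied to the end of treatment, when no ADAS-Cog is given; its 3-point cut fits only the 12-month visit, which the rule does not name

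*Combined protocol and SAP*

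**What the plan says.** Section 3.10 classifies patients on the ADAS-Cog: "patients who have an increase of no more than 50% (~3 points) on the ADAS-Cog at the end of treatment will be considered responders". It adds: "This is equivalent to a delay in decline of about 6-8 months". The cut comes from the trial described just before, in which "a significant benefit in the active group was considered to be a 50% reduction in cognitive decline as indicated by change in ADAS-Cog score". The figures quoted for that trial's placebo patients are 24.2 (SD 9.4) at baseline and 29.9 (SD 13.7) later, a change of 5.7 (SD 8.2) over one year.

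On the length of treatment, Section 3.8.4 says: "This dose will be delivered in 5 fractions or 10 fractions of 2 Gy". Section 2.4 schedules the cognitive tests "at baseline and at 6 weeks, 3 months, 6 months, and 12 months during follow-up". The Study Calendar (Section 6.0) agrees. Its first ADAS-Cog after baseline is in the column headed "6 Weeks Post Treatment +/- 1 week", and its daily-radiation column is marked for toxicity evaluation only.

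Section 3.10 also plans a model: "Longitudinal analysis will be carried out for each individual patient using a fixed quadratic effect of time". Section 3.1 declares all endpoint assessment descriptive, with 15 patients per cohort, and Section 3.2 has no control arm.

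**The concern.** The rule names a moment with no ADAS-Cog score. Someone applying it has to choose a visit, and the choice changes the answer. A cut equal to half of a year's decline is easier to meet after six weeks or six months than after twelve months, because untreated patients have had less time to decline.

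The testers are not blinded (Section 3.10) and there is no concurrent control, so a visit chosen after the data are in would be hard to defend. Secondary objective 1 asks whether the intervention changes the course of the disease, and Section 3.1 says that the pilot is to inform a larger study. A responder proportion with no stated visit would inform that study poorly.

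**Working it through.** **Inputs.** Mean one-year change 5.7, SD 8.2, baseline 24.2 (SD 9.4), later score 29.9 (SD 13.7), cut about 3 points: all Section 3.10. Visits: Sections 2.4, 3.10 and 6.0. Cohort size 15: Section 3.1.

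**1. The plan's own figures.** 29.9 − 24.2 = 5.7, and half of 5.7 is 2.85, which rounds to 3. If decline is linear, the delay is 2.85/5.7 × 12 = 6.0 months, or 3/5.7 × 12 = 6.3 months at a cut of 3. This is the lower end of the stated 6 to 8 months. The cut reproduces, as half of a 12-month decline.

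**2. Which visit fits.** With linear decline, the mean untreated change at 6 months is 5.7 × 6/12 = 2.85. A 3-point increase at that visit is therefore ordinary decline and shows no delay. A delay of 6 to 8 months can be seen only at the 12-month visit.

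**3. Rate at 12 months** (normal changes, cut 3).
- No effect: Φ((3 − 5.7)/8.2) = Φ(−0.329) = 37.1%, or 5.6 of 15. With a cut of 2.85 it is 36.4%.
- True halving: Φ((3 − 2.85)/8.2) = 50.7%, or 7.6 of 15.

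**4. No-effect rate at earlier visits.** The documents give no interim SDs, so three models are assumed with linear decline. The figures are illustrative and are not bounds.

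| Visit | Mean change | SD constant at 8.2 | SD by root of time | SD proportional to time |
|---|---|---|---|---|
| 6 months | 2.85 | 51% | 51% | 51% |
| 3 months | 1.43 | 58% | 65% | 78% |
| 6 weeks (1.5 months) | 0.71 | 61% | 78% | 99% |

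**5. How firm the 37% is.**
- Mean decline 2 points lower (3.7) or higher (7.7), SD 8.2: 46.6% and 28.3%.
- Right-skewed changes with the same mean and SD (Pearson type III, skewness 0.5 to 1.5): 40% to 46%.

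**6. What 15 patients can show.** The exact 95% CI is 16% to 68% for 6/15 and 27% to 79% for 8/15. Both contain 37% and 51%. The chance of 8 or more responders is 15% with no effect and 52% with a true halving.

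**7. Missing 12-month scores.** The instrument-development article appended to the protocol reports that missing data rose with severity and length of follow-up. In its Table 1 (sum of word-list trials), the MMSE 16–20 group falls from 47 to 40 scored patients and the MMSE 10–15 group from 45 to 29. Together that is 69 of 92, or 75%, over the same MMSE range that this trial enrols. If 75% also held here (an assumption), about 11 of 15 would have a score. A true 37.1% would then read as follows:
- among scored patients, if every missing patient was a non-responder: 0.371/0.75 = 49.5%
- over all treated patients with missing counted as non-response, if missingness is unrelated to response: 0.371 × 0.75 = 27.8%

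**8. The cited range.** With a mean of 24.2 and all scores between 13 and 26, the largest possible SD is √((24.2 − 13)(26 − 24.2)) = √20.16 = 4.49. The quoted SD is 9.4. The other figures agree with each other: the three SDs imply a baseline-to-later correlation of (9.4² + 13.7² − 8.2²)/(2 × 9.4 × 13.7) = 0.81. The range is the figure that does not fit.

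**The case against.** The strongest reply is that the meaning can be recovered. The cut is derived from a one-year decline in the sentences just before the rule, and the section's heading speaks of assessment during treatment although it schedules only post-treatment tests. The word treatment may therefore be loose, with 12 months intended. That is plausible, but the text does not say it. The same section dates the tests as after treatment, and Sections 3.1 and 3.11 count follow-up from completion of treatment.

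The early-visit rates also deserve discounting. They assume linear decline, whereas Section 3.10 plans a quadratic time effect, and the proportional-SD model leaves almost no test-retest error at 6 weeks. The match at 51% between no effect at 6 months and a true halving at 12 months is built in, because both have a mean change of 2.85. What stands is the direction: an earlier visit makes the cut easier to meet.

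A reader might go further in four ways that the documents do not support.
- That 50% means half of the patient's own score, 12.1 points at a baseline of 24.2. The parenthesis giving about 3 points rules this out.
- That leaving out a no-effect rate is an error. The study is declared descriptive, and Section 3.10 already gives the placebo mean and SD. The rate is useful context only.
- That 37% is a firm benchmark. It rests on normality and on a historical group described as "In a large clinical trial the baseline score for placebo-treated patients in the ADAS-Cog range of 13 to 26 was" 24.2, with an SD that cannot occur in that range.
- That the faulty range undermines the cut. It enters neither the 3 points nor the 37%.

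**Conclusion.** The rule is wrong as written: it refers to a time with no ADAS-Cog score, and its cut matches only the 12-month visit. Both follow from the schedule and the plan's own arithmetic, without modelling.

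The size depends on assumptions. With normal changes and the quoted 5.7 and 8.2, the no-effect rate is about 37% at 12 months (28% to 47% if mean decline differs by 2 points, 40% to 46% with right skew). With linear decline it is about 51% at 6 months and higher before that. The 37% applies to complete data, and a cohort of 15 cannot distinguish it from the 51% of a true halving.

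A reader might infer that the trial will report most untreated-type patients as responders. The documents do not support that, since they never choose an early visit; they only fail to exclude one. Nor does the defect reach safety decisions. No stopping rule in Section 3.12 and no escalation step uses the responder rate, and the planned longitudinal analysis does not depend on it. The effect is on how one descriptive secondary result is read.

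**What to change.** 1. In Section 3.10, define a responder as a patient whose ADAS-Cog increases from baseline by no more than 3 points at the 12-month visit. Drop the percentage.
2. For each cohort, report the number of responders over all treated patients, counting a missing 12-month score as non-response. Beside it, report the proportion among patients with a score. Give each an exact 95% CI, and state the number missing. Say how patients replaced or excluded under Section 3.9 enter the first denominator, which may then exceed 15.
3. As context, state that the quoted 5.7 and SD 8.2 imply roughly 37% responders with no effect under normality, with the ranges above. Say that the figure is historical, that it applies to complete data, and that 15 patients cannot separate it from the 51% of a true halving.
4. Separately, check the range of 13 to 26 against the cited source. The documents cannot show what it should be, and the cut does not depend on it.

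The cost is a few sentences and one citation check; no visits, patients or data are added. The downside is that the responder rate will look less favourable at 12 months than at an earlier visit, and less favourable again with missing scores counted as non-response.
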